7.3.8 Dose Delays/Modifications

Dose Modifications for Adverse Reactions

The recommended abemaciclib dose modifications for adverse events are provided in table below. Discontinue abemaciclib for participants unable to tolerate 50 mg twice daily. Once the drug is reduced, there is no dose re-escalation.

Abemaciclib Dose Modification for Adverse Reactions

| Dose Level | Abemaciclib Dose |
|---------------------------|--------------------|
| Recommended starting dose | 200 mg twice daily |
| First dose reduction | 150 mg twice daily |
| Second dose reduction | 100 mg twice daily |
| Third dose reduction | 50 mg twice daily |

Guidelines for Dose Adjustments and Delays of Abemaciclib

| Toxicity Type | Toxicity Profile and Severity | Dose Modification | Dose Reduction |
|--------------------------------------------------|----------------------------------|---------------------------------------------------------|------------------------------------------------------------------------------------------------------------------------------------------|
| Hematologic Toxicity | Grade 3 | Dose MUST be held until toxicity resolves to ≤ Grade 2. | Dose MAY be reduced by 1 dose level at investigator's discretion. |
| Hematologic Toxicity (second or more recurrence) | Grade 3 | Dose MUST be held until toxicity resolves to ≤ Grade 2. | Dose MUST be reduced by 1 dose level with each occurrence. Discontinue abemaciclib for participants unable to tolerate 50 mg twice daily |
| Hematologic Toxicity | Grade 4 | Dose MUST be held until toxicity resolves to ≤ Grade 2. | Dose MUST be reduced by 1 dose level. Discontinue abemaciclib for participants unable to tolerate 50 mg twice daily |

| Nonhematologic Toxicity (except diarrhea and ALT increased) | Persistent or recurrent Grade 2 that does not resolve with maximal supportive measures within 7 days to baseline or Grade 1 | Dose MUST be held until toxicity resolves to either baseline or ≤ Grade 1. | Dose MUST be reduced by 1 dose level. Discontinue abemaciclib for participants unable to tolerate 50 mg twice daily |
|----------------------------------------------------------------------|-----------------------------------------------------------------------------------------------------------------------------|----------------------------------------------------------------------------|-----------------------------------------------------------------------------------------------------------------------------|
| Nonhematologic Toxicity (except diarrhea and ALT increased) | Grade 3 or 4 that does not resolve with maximal supportive measures within 7 days to baseline or Grade 1 | Dose MUST be held until toxicity resolves to either baseline or ≤ Grade 1. | Dose MUST be reduced by 1 dose level. Discontinue abemaciclib for participants unable to tolerate 50 mg twice daily |
| Diarrhea | Grade 2 that does not resolve within 24 hrs to at least Grade 1 | Dose MUST be held until toxicity resolves to \(\leq \text{Grade} \) 1. | Dose MAY be reduced by 1 dose level. |
| Diarrhea | Grade 3 or 4 that does not resolve with maximal supportive measures within 7 days or requires hospitalization. | Dose MUST be held until toxicity resolves to ≤ Grade 1. | Dose must be reduced by 1 dose level - Discontinue abemaciclib for participants unable to tolerate 50 mg twice daily |

| ALT/AST increased | Grade 2 (>3.0-5.0xULN) that does not resolve within 7 days to baseline or < Grade 1 | Dose MUST be held until toxicity resolves to baseline or Grade 1 | Dose MUST be reduced by 1 dose level |
|-------------------|-------------------------------------------------------------------------------------|------------------------------------------------------------------|------------------------------------------|
| | Grade 3 (>5.0-20.0xULN) with total bilirubin >2xULN, in the absence of cholestasis | Abemaciclib therapy MUST be discontinued | Abemaciclib therapy MUST be discontinued |
| | Grade 4 (>20.0xULN) | Abemaciclib therapy MUST be discontinued | Abemaciclib therapy MUST be discontinued |

Abbreviations: ALT = alanine aminotransferase, AST=aspartate aminotransferase, ULN = upper limit of normal.

Monitor ALT, AST, and serum bilirubin prior to the start of abemaciclib therapy, every 2 weeks for the first 2 months, monthly following cycle 2, and as clinically indicated.

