7.4.5 General Guidance for Interstitial lung disease (ILD)/Pneumonitis events

Interstitial lung disease (ILD) / pneumonitis has been identified as an adverse drug reaction for abemaciclib. Adverse events reported included events such as interstitial lung disease, pneumonitis, obliterative bronchiolitis, organizing pneumonia, pulmonary fibrosis. The majority of events were Grade 1 or Grade 2 with serious cases and fatal events reported.

Monitor for clinical symptoms or radiological changes indicative of ILD/pneumonitis and please ask patients to report any new or worsening pulmonary symptoms. Symptoms may include hypoxia, cough, dyspnea, or interstitial infiltrates on radiologic exams.; these symptoms should be investigated and treated as per local clinical practice and/or guidelines (including corticosteroids as appropriate). Infectious, neoplastic, and other causes for such symptoms should be excluded by means of appropriate investigations. Investigations may include imaging such as high resolution computer tomography (HRCT), bronchoalveolar lavage (BAL), and biopsy as clinically indicated (see also Table 7: refer to dose adjustment table for interstitial lung disease/pneumonitis).

Dose Modification and Management — Interstitial Lung Disease/Pneumonitis

| ose mounication and managem | ent interstitut Eung Disease/I neumonitis |
|--------------------------------------------------------------------------------------------------------------------------------------|--------------------------------------------------------------------------------------|
| CTCAE Grade | Abemaciclib Dose Modifications |
| Grade 1 or 2 | No dose modification is required. |
| Persistent or recurrent Grade 2 toxicity that does not resolve with maximal supportive measures within 7 days to baseline or Grade 1 | Hold dose until toxicity resolves to baseline or Grade 1. Resume at next lower dose. |
| Grade 3 or 4 | Discontinue abemaciclib. |

Dose Modification and Management — Nonhematologic Toxicities Excluding Diarrhea, ALT Increased, and ILD/Pneumonitis

| CTCAE Grade | Abemaciclib Dose Modifications |
|---------------------------------------------------------------------------------------------------------------------------------------------------|---------------------------------------------------------------------------------------|
| Grade 1 or 2 | No dose modification is required. |

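### AST falls under both the general nonhematologic rows and the ALT/AST rows, which prescribe different actions, and no rule says which governs

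*Combined protocol and SAP*

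**What the plan says.** Section 7.3.8 has two general rows for nonhematologic toxicity, one for Grade 2 and one for Grade 3 or 4. Both carry the label "Nonhematologic Toxicity (except diarrhea and ALT increased". The Grade 3 or 4 row is triggered by "Grade 3 or 4 that does not resolve with maximal supportive measures within 7 days to baseline or Grade 1". Its two actions are "Dose MUST be held until toxicity resolves to either baseline or ≤ Grade 1" and "Dose MUST be reduced by 1 dose level. Discontinue abemaciclib for participants unable to tolerate 50 mg twice daily".

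Further down, the same table has rows labelled "ALT/AST increased". The one for "Grade 4 (>20.0xULN" has no waiting period and says "Abemaciclib therapy MUST be discontinued". The same instruction applies to a Grade 3 rise (>5 to 20×ULN) when total bilirubin exceeds 2×ULN and there is no cholestasis. The Grade 2 row (>3 to 5×ULN) calls for a hold and a one-level reduction if the rise has not settled within 7 days.

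Section 7.4.5 has a second general table, headed "Nonhematologic Toxicities Excluding Diarrhea, ALT Increased, and ILD/Pneumonitis".

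Section 10.1.1 adds a separate rule. Possible drug-induced liver injury, defined as AST or ALT at least 3×ULN with either bilirubin at least 2×ULN or INR above 1.5, requires treatment to stop at once and an SAE report.

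**The concern.** The protocol separates toxicities that have their own rules from the general rows by naming them in the label. Diarrhea and ALT are named in 7.3.8; ILD/pneumonitis is added in 7.4.5, where it has its own table. AST has its own rows but is named in neither place. Read literally, AST is governed twice, and at the higher grades the two rules differ: one ends treatment, the other allows it to resume one level lower.

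The row used decides whether a participant is re-exposed after a severe liver-enzyme event. It also decides whether that participant appears in the summary of AEs leading to withdrawal planned in section 8.5.2. In a study this small, one participant is visible in that summary: 1/20 = 5 percentage points if 20 are treated, and 1/10 = 10 points if 10 are.

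**Working it through.** There is no plan figure to reproduce and no sample-size or power quantity is involved. The check is to apply each rule to an AST rise, grade by grade.

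| AST event | ALT/AST rows, 7.3.8 | General rows, 7.3.8 | Do they agree? |
|---|---|---|---|
| Grade 2, unresolved at 7 days | Hold, reduce one level | Hold, reduce one level | Yes, in substance |
| Grade 3, isolated | No action given | Hold and reduce, if unresolved at 7 days | Only one rule speaks |
| Grade 3, bilirubin >2×ULN, no cholestasis | Discontinue | Hold and reduce, if unresolved at 7 days | No, once 7 days have passed |
| Grade 4 | Discontinue | Hold and reduce, if unresolved at 7 days | No, once 7 days have passed |

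Isolated here means without bilirubin above 2×ULN and outside the section 10.1.1 definition.

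1. **The same events for ALT.** The general column drops out because ALT is excepted. A Grade 4 ALT rise meets only the discontinuation row, so the double match is specific to AST.

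2. **Section 7.4.5.** The heading is legible and leaves AST in. The row that includes Grade 3 or 4 appears to say hold, then resume at the next lower dose. In the text as read from the PDF, the Grade 3 or 4 label runs into the Grade 2 cell, so it cannot be established whether the higher grades carry their own 7-day condition.

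3. **Section 10.1.1 against the Grade 3 row.** AST above 5×ULN satisfies at least 3×ULN, and bilirubin above 2×ULN satisfies at least 2×ULN. Every event in that row therefore meets the numerical part of the 10.1.1 definition. Where the event is judged possible drug-induced liver injury, 10.1.1 points the same way as the specific row. It does not reach an AST rise with neither bilirubin nor INR raised to its limits.

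4. **Precedence.** No sentence in 7.3.8, 7.4.5 or 10.1.1 says that a specific row overrides a general one.

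5. **Frequency.** The laboratory table for the 200 mg monotherapy breast cancer study (section 2.4.2, Table 4, N = 132) gives AST increased as 4% at Grade 3 and 0% at Grade 4. It does not separate Grade 3 rises by bilirubin or by duration. The documents give no rate for biliary cancer.

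**The case against.** The best defence is timing. In 7.3.8 the discontinuation rows apply at onset, whereas the general row needs 7 unresolved days. An investigator who follows the row that names AST has already stopped treatment before the general row can apply. That stands. A reader might infer that 7.3.8 issues opposite orders the moment AST reaches Grade 4; it does not. The overlap in that table concerns a persisting rise. Section 3.4 may narrow it further, since it withdraws participants whose possibly related toxicity has not resolved in 14 days, though its order relative to the hold instruction is not stated.

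It is also fair to say that a specific row would ordinarily be taken to control. The protocol does not say so, however, and its own method of separating rules is the named exception, which omits AST each time.

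The defence is right that Grade 2 AST is not in conflict and that section 10.1.1 covers much of the Grade 3-with-bilirubin case. It is right, too, that one instruction for isolated Grade 3 AST is not a contradiction. What remains there is different: the instruction exists only if the general row governs AST.

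A reader might also convert the 4% Grade 3 rate into a sizeable chance that the conflict will occur among 10 to 20 participants. The documents do not support that. The 4% counts every Grade 3 AST rise, including isolated ones where the rows do not contradict each other, while the clearest conflict is at Grade 4, reported as 0% of 132.

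**Conclusion.** The inconsistency is real and limited. It lies in three labels: the two general rows of 7.3.8 and the table heading in 7.4.5. Its effects are:

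- two incompatible mandatory actions for a Grade 4 AST rise that persists to 7 days;
- the same double match for Grade 3 AST with bilirubin above 2×ULN and no cholestasis, largely covered by section 10.1.1;
- an isolated Grade 3 AST rise whose only tabled action depends on an unstated rule of precedence.

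The first is expected to be rare if the cited monotherapy data are a guide, which is an assumption, since they come from breast cancer. The frequency in this population cannot be derived from the documents.

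Two further inferences should be resisted. Section 7.4.5 cannot be relied on as an unconditional resume rule for Grade 4, because its cell boundaries are unclear in the available text. Nor do the documents show an effect on the response-rate endpoint; the consequences identified are for safety, exposure and the withdrawal summary. The point is an inconsistency between passages, not a questionable design choice. It deserves correction because the labels direct dosing and cost little to align.

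**What to change.** Reconcile the general-row labels in 7.3.8 and the table heading in 7.4.5 with the ALT/AST rows and with section 10.1.1, and state which row governs AST at each grade. The four cases to settle are Grade 2, isolated Grade 3, Grade 3 with raised bilirubin, and Grade 4.

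Adding AST to the exception would not be enough by itself. It would remove the only tabled action for an isolated Grade 3 AST rise, so if that route is taken the sponsor must also state what applies there. Which clinical action is appropriate is for the sponsor to decide.

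The cost is a few words in three labels and a sentence or two on precedence, made through the amendment process in section 11.1. Sample size, assessments and analyses need not change.

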7.1.6 Dosing Adjustments, Delays and Discontinuation

Abemaciclib Dose Modification for Grade 3 or 4 AEs

| Dose Level | Abemaciclib Dose |
|---------------------------|--------------------|
| Recommended starting dose | 200 mg twice daily |
| First dose reduction | 150 mg twice daily |
| Second dose reduction | 100 mg twice daily |
| Third dose reduction | 50 mg twice daily |

Complete blood counts with differentials and complete metabolic panel will be monitored every 2 weeks for the first 2 months, then monthly for the next 2 months, at the beginning of every cycle.

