| Persistent or recurrent Grade 2 toxicity that does not resolve with maximal supportive measures within 7 days to baseline or Grade 1 Grade 3 or 4 | Hold dose until toxicity resolves to baseline or Grade 1. Resume at next lower dose. |

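### The Section 7.3.8 dosing table does not exclude ILD/pneumonitis, so for Grade 3 or 4 events it conflicts with the discontinuation rule in Section 7.4.5

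*Combined protocol and SAP*

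**What the plan says.** Section 7.3.8 introduces its table as the source of dose modifications for adverse events generally. It has two nonhematologic rows, both titled "Nonhematologic Toxicity (except diarrhea and ALT increased" (closing bracket omitted). The first covers persistent or recurrent Grade 2 events. The second is triggered by "Grade 3 or 4 that does not resolve with maximal supportive measures within 7 days to baseline or Grade 1"; the dose is then held until the event is back to baseline or Grade 1, and reduced by one level. Under that row the drug is stopped for good only if 50 mg twice daily cannot be tolerated.

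Section 7.4.5 deals with ILD and pneumonitis, which it calls an identified adverse drug reaction. On severity it states: "The majority of events were Grade 1 or Grade 2 with serious cases and fatal events reported". Its ILD table reads, for the top grades, "Grade 3 or 4 | Discontinue abemaciclib". There is no waiting period and no route back to dosing. The text of 7.4.5 tells the reader to "refer to dose adjustment table for interstitial lung disease/pneumonitis".

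Section 3.4 lists the grounds for withdrawing a participant from treatment. They include toxicity the Principal Investigator judges unacceptable, the participant's best medical interest, and possibly related toxicity that has not resolved in 14 days.

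**The concern.** Pneumonitis is a nonhematologic toxicity and is not among the two exclusions, so at Grade 3 or 4 it belongs in the 7.3.8 row as written. For the same event, one table waits, holds and resumes, while the other stops the drug permanently. Both cannot be followed.

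At stake is re-exposure of a participant to abemaciclib after severe or life-threatening lung toxicity that the protocol itself links to deaths. Section 7.3.8 is also the table that staff are directed to: the diarrhea guidance in 7.4.1 sends the reader back to it. A person who looks up pneumonitis there finds a row that appears to apply, and nothing to suggest a different rule exists.

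**Working it through.** The plan gives no figure on this point, so the check is a comparison of instructions.

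**1. Does Grade 3 or 4 ILD fall in the 7.3.8 row?** The row title excludes diarrhea and ALT only. No other row mentions lung toxicity. It does.

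**2. Is the missing exclusion deliberate?** Probably not. The second table in 7.4.5 covers other nonhematologic toxicities, and its title excludes diarrhea, ALT and also ILD/pneumonitis. The 7.3.8 title has the first two exclusions but lacks the third. Section 7.3.8 also states permanent discontinuation where it is wanted: its ALT/AST rows require it at Grade 4, and at Grade 3 with bilirubin above twice the upper limit of normal. The absence of any such entry for ILD could be read as meaning that stopping is not required.

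**3. Where do the two rules diverge?** Take Grade 3 or 4 pneumonitis, possibly related to the drug, in a participant on 200 mg twice daily. Section 3.4 does not say when its 14 days start or what grade counts as resolved. I assume counting from onset, and resolution to baseline or Grade 1.

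| Course of the event | 7.3.8 read literally | 7.4.5 ILD table |
|---|---|---|
| Resolves within 7 days | No mandatory hold or reduction | Discontinue |
| Unresolved at day 7, resolves by day 14 | Hold, then resume at 150 mg twice daily | Discontinue |
| Unresolved at day 14 | On hold; withdrawn under 3.4 | Discontinue |

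The rules reach the same end only in the last line. In the first two, 7.3.8 allows treatment that 7.4.5 forbids.

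**4. How far apart are they in dose?** Before the 7.3.8 hold becomes mandatory: 2 doses a day × 7 days = 14 doses, or 14 × 200 mg = 2,800 mg. Dose on resumption: 150/200 = 75% of the starting dose. Under 7.4.5 both are zero. These are the most that 7.3.8 leaves open, not what it orders.

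**5. Is Grade 2 affected?** No. For persistent or recurrent Grade 2 events both sections hold to baseline or Grade 1 and resume one level lower. The conflict is confined to Grade 3 and 4.

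**6. Does anything else settle it?** The pointer "refer to dose adjustment table for interstitial lung disease/pneumonitis" sits inside 7.4.5, so it helps only a reader who is already there. The ladder in 7.1.6, headed "Abemaciclib Dose Modification for Grade 3 or 4 AEs", merely defines dose levels. It has no ALT/AST exception either, so its silence on ILD shows nothing. No sentence ranks 7.4.5 above 7.3.8.

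**The case against.** The strongest reply is that the protocol already contains the right rule. Section 7.4.5 is specific to ILD, its table is explicit, and a careful reader would follow the specific over the general. Section 7.3.8 does not order continued dosing, and Section 3.4 gives the investigator several grounds to stop at any time. This is a single-center study (7.1.3) with monthly staff meetings that cover drug safety (11.2). All of that stands and makes an actual error less likely. It does not remove the conflict: discretion permits stopping, whereas 7.4.5 requires it, and a mandatory safety rule should not depend on staff inferring which table prevails.

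Three stronger readings are tempting, and the documents do not support them.

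- *A probability of harm.* A reader might carry over the 2 pneumonitis deaths among 441 patients in MONARCH 2 (2.4.2). That counts fatal cases, which are never re-treated, whereas the conflict concerns cases that resolve. MONARCH 2 also used 150 mg with fulvestrant, over a median of 12 months. In MONARCH 1, at the 200 mg dose used here, the reported deaths were attributed to infection, and none of the ten listed discontinuations was for ILD. Neither study gives a rate for resolving Grade 3 or 4 ILD.
- *A general failure to hold at onset.* The hematologic rows hold at once, with the reduction after a first Grade 3 event optional ("Dose MAY be reduced by 1 dose level at investigator's discretion"), while the nonhematologic row waits 7 days. For toxicities other than ILD, that is a dosing trade-off left to investigator judgement. The 7.4.5 table that might contradict it has cells run together in the available text ("within 7 days to baseline or Grade 1 Grade 3 or 4"), so no conflict can be shown. Rewriting both to match could also loosen the step-down on resumption in that 7.4.5 table.
- *Withdrawal under 3.4 only after 14 days.* Section 3.4 lists several other grounds.

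**Conclusion.** The inconsistency is real and rests on text that is intact in both places. For Grade 3 or 4 ILD/pneumonitis that resolves within 14 days, 7.3.8 read literally allows re-treatment that 7.4.5 rules out. The intended rule is clear from 7.4.5; the defect is that 7.3.8 neither states it nor points to it. The size is a difference in instruction (permanent stop versus possible resumption at 75% of the starting dose or, after resolution within 7 days, no mandatory reduction), not an estimated number of participants. The 14-day boundary depends on the reading of 3.4 given above. The point should be fixed because the reaction can be fatal and the correction is almost free. It does not extend to other nonhematologic toxicities or to the diarrhea rows.

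**What to change.** Amend Section 7.3.8 in two ways:

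1. Retitle both nonhematologic rows so that the exclusions are diarrhea, ALT increased and ILD/pneumonitis.
2. Add an ILD/pneumonitis row stating that abemaciclib is discontinued at Grade 3 or 4, or add a cross-reference to the ILD table in 7.4.5.

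The cost is a wording amendment to one table. It adds no procedures, leaves dosing for every non-ILD event unchanged, and makes 7.3.8 say what 7.4.5 already requires.

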7.1.5 Study Treatment

Abemaciclib will be given as a single oral agent. The starting dose will be 200 mg twice daily. One cycle = 28 days. There will be no protocol scheduled hiatus and daily dosing will be continuous unless there is unacceptable toxicity, disease progression, or death.

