7.4 Supportive Care Guidelines

7.4.1 Guidelines for Diarrhea Management

Clinical trial data indicates the majority of patients who receive abemaciclib will develop diarrhea. Early identification and intervention for the management of diarrhea has been helpful to patients

At enrollment, participants should receive instructions on the prompt management of diarrhea. In the event of diarrhea, supportive care measures should be initiated as early as possible. These include the following:

- At the first sign of loose stools, the participant should initiate antidiarrheal therapy (e.g. loperamide) and notify the investigator for further instructions and appropriate follow-up.
- Participants should also be encouraged to drink fluids (e.g., 8 to 10 glasses of clear liquids per day).
- Site personnel should assess response within 24 hours.
- (Refer to Dose Modification Table above for more information on dose modification).

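### Section 7.3.8 forces a diarrhea hold at 24 hours for Grade 2, but only after 7 days for Grade 3 or 4 managed without hospitalization

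*Combined protocol and SAP*

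**What the plan says.** The dose-adjustment table in section 7.3.8 has two rows for diarrhea. The lower row is triggered by "Grade 2 that does not resolve within 24 hrs to at least Grade 1"; the hold is then mandatory and a one-level reduction optional. The higher row is triggered by "Grade 3 or 4 that does not resolve with maximal supportive measures within 7 days or requires hospitalization"; both the hold and the reduction are then mandatory. Either hold lasts until Grade 1 or lower. The section adds: "Once the drug is reduced, there is no dose re-escalation".

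Section 7.4.1 warns that most patients on abemaciclib get diarrhea. It asks the participant to start an antidiarrheal and notify the investigator at the first loose stool, and adds: "Site personnel should assess response within 24 hours". For dosing it points back to the same table: "Refer to Dose Modification Table above for more information on dose modification". The default is set in section 7.1.5: "daily dosing will be continuous unless there is unacceptable toxicity, disease progression, or death".

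**The concern.** A dose-hold table should act at least as early for a worse event as for a milder one. Here the reduction column is in the right order (optional at Grade 2, mandatory at Grade 3 or 4), but the hold timing runs the other way. Followed literally, the 24-hour check in 7.4.1 forces a hold for persistent Grade 2 and forces nothing for persistent Grade 3 in a participant still at home. An early hold for that participant rests on discretion alone, for a toxicity the protocol expects in most patients. The table is also silent on which row governs when Grade 2 becomes Grade 3.

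**Working it through.** **1. Compare the hold triggers.**

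| Toxicity | Grade 2 | Grade 3 or 4 |
|---|---|---|
| Diarrhea (7.3.8) | above Grade 1 after 24 hours | unresolved after 7 days, or hospitalization |
| Other nonhematologic (7.3.8) | unresolved after 7 days | unresolved after 7 days |
| Hematologic (7.3.8) | no hold row | hold, no waiting period |
| ILD/pneumonitis (7.4.5) | unresolved after 7 days | discontinue |

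The ALT/AST rows state no waiting time at Grade 3 or 4, so they are not comparable. Where a waiting time is stated at both levels, only diarrhea gives the worse grade the longer one: 7 × 24 = 168 hours against 24, a ratio of 7.

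**2. Look for another rule that closes the gap.** The general nonhematologic rows in 7.3.8 and the second table in 7.4.5 both exclude diarrhea. Section 7.4.1 has no hold rule of its own. Section 7.1.6 lists dose levels without hold timing. The fixed rule in 3.4 on unresolved toxicity acts at 14 days, which is later. What remains is judgement: unacceptable toxicity (7.1.5 and 3.4) and the participant's best medical interest (3.4).

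**3. Doses taken before a hold becomes mandatory** (days × 2 doses per day × dose, at the 200 mg starting dose in 7.1.5).
- Grade 2: 1 × 2 = 2 doses; 2 × 200 = 400 mg.
- Grade 3 or 4, not hospitalized: 7 × 2 = 14 doses; 14 × 200 = 2,800 mg.
- Largest difference: 12 doses; 12 × 200 = 2,400 mg, or 12 × 50 = 600 mg at the lowest dose level.

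This difference is reached only if nobody holds earlier.

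**4. How many participants might have Grade 3 diarrhea.** The protocol gives no rate for biliary tract cancer. As an assumption, take the Grade 3 rates in its own tables: 20% in MONARCH 1 (200 mg twice daily alone, Table 3) and 13% in MONARCH 2 (150 mg twice daily with fulvestrant, Table 1). Grade 4 was 0% in both. The trial needs 10 evaluable participants and may enroll about 20.

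| Rate | Expected of 10 | Chance of at least one | Expected of 20 | Chance of at least one |
|---|---|---|---|---|
| 13% | 10 × 0.13 = 1.3 | 1 − 0.87^10 = 0.75 | 20 × 0.13 = 2.6 | 1 − 0.87^20 = 0.94 |
| 20% | 10 × 0.20 = 2.0 | 1 − 0.80^10 = 0.89 | 20 × 0.20 = 4.0 | 1 − 0.80^20 = 0.99 |

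These are expected counts, not limits. At 20%, the binomial chance of more than 2 of 10 is 0.32, and of more than 4 of 20 is 0.37. They also count every Grade 3 case. The documents do not say what share would stay outpatient and unresolved at 24 hours, and that share could be zero.

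**The case against.** The strongest reply is that the mandatory hold is a minimum. Nothing forbids stopping sooner, 7.3.8 describes its modifications as recommended, the investigator is told at the first loose stool, and response is checked within 24 hours. Diarrhea led to discontinuation in 1 of 132 MONARCH 1 patients, at this trial's dose, and in 1% in MONARCH 2. That stands as evidence that the toxicity is usually manageable. It does not show that a 7-day wait is safe, because the documents do not give those trials' hold rules. Nor does it explain why the milder grade gets a mandatory early hold while the worse grade is left to judgement.

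The sponsor could add that 7 days is its ordinary limit, since the general nonhematologic row reads "Grade 3 or 4 that does not resolve with maximal supportive measures within 7 days to baseline or Grade 1". But that row excludes diarrhea, and its Grade 2 counterpart also waits 7 days, so nothing is inverted there.

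Two further points narrow the gap, and both stand. Grade 2 that has already lasted 24 hours arguably stays held until Grade 1 or lower even if it worsens. Hospitalization already triggers a hold, which should capture many of the worst cases. The row nevertheless offers hospitalization as an alternative trigger, so it foresees Grade 3 or 4 without it.

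A reader might infer that the protocol contradicts itself because the second table in 7.4.5 appears to hold Grade 3 or 4 with no wait. The available text of that table merges the Grade 2 and Grade 3 or 4 cells, and the table excludes diarrhea, so no weight is placed on it.

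**Conclusion.** The inversion is real as written and should be corrected. It concerns chiefly outpatient Grade 3 diarrhea at or near onset. For such a participant the written rule allows up to 14 doses before a mandatory hold, against about 2 at Grade 2. The expected number with any Grade 3 diarrhea is 1.3 to 2.0 of 10 or 2.6 to 4.0 of 20, provided the breast cancer rates carry over. The number actually exposed is smaller by an unknown amount.

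Three stronger readings are not supported. The protocol does not require dosing to continue through 7 days of Grade 3 diarrhea; it only fails to require a hold. The expected counts cannot be read as the number exposed, or as a ceiling on Grade 3 cases. No statistical result of the trial is put in doubt: this is a participant-safety dosing rule.

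**What to change.** In 7.3.8, change the trigger of the higher diarrhea row to *Grade 3 or 4 of any duration, or any grade requiring hospitalization*, with a mandatory hold from onset until Grade 1 or lower. Keep that row's reduction column as it is: a mandatory one-level reduction, with discontinuation if 50 mg twice daily is not tolerated. Add one line: *if diarrhea worsens, the higher-grade row applies at once, and a hold already in force continues until Grade 1 or lower.* Repeat the hold at onset in 7.4.1.

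No visits, tests or participants are added. The cost is dose intensity. A cycle has 28 × 2 = 56 doses; for an assumed hold of 1 to 7 days the loss is 2/56 = 3.6% to 14/56 = 25% of a cycle. In addition, some participants whose Grade 3 diarrhea would have cleared within 7 days will take a one-level reduction, permanent because re-escalation is not allowed. If the sponsor prefers not to force those reductions, the hold at onset alone still corrects the inversion.
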